7. ADVERSE EVENTS AND TOXICITY MANAGEMENT

7.1. Dose Limiting Toxicities

Determination of DLTs occurs only during the DLT periods defined in Section 3 for Cohorts A1, B1, and C1. See Study Procedures for DLT definitions.

7.2. Modification or Holding of Dose for Toxicities

Doses of MS-553 can be decreased or held for toxicities for events deemed possibly, probably, or definitely related to MS-553. Refer to Section 6.1.7, Dose modifications and dose delay and Appendix 2A: MS-553 Recommended Dose Modifications and Delays for Toxicity, Appendix 2B and Appendix 2C for more information and specific guidance. The dose of MS-553 that is restarted could be reduced if the investigator feels it prudent to re-challenge at a lower dose, and if the same toxicity does not recur approximately after four weeks, the dose may be increased back to the patient's prior dose. Discussion with the medical monitor/Sponsor are needed for such dose modifications.

7.3. Adverse Events

Any untoward medical occurrence in a patient or clinical investigation subject administered a pharmaceutical product and which does not necessarily have to have a causal relationship with this treatment. An adverse event (AE) can therefore be any unfavorable and unintended sign (including an abnormal laboratory finding, for example), symptom, or disease temporally associated with the use of a medicinal product, whether or not considered related to the medicinal product (FDA Guidance for Industry 1995). In addition, AEs may also represent pre- or post-treatment complications that occur as a result of protocol-specified procedures. For the purposes of this clinical study, AEs shall include events which are either new or represent detectable worsening of pre-existing conditions that occur as a consequence of participation in the clinical study. The following are expressly not considered AEs:

Pre-existing conditions

- Pre-existing conditions (documented in the medical history CRF) unless the severity, frequency, or character is exacerbated during the study period
- Hospitalization except for elective hospitalizations that had been planned for preexisting conditions that have not worsened. However, if the pre-planned hospitalization is lengthened as a result of participation in the study or if during the pre-planned hospitalization an adverse event, meeting SAE criteria, occurs then the event(s) are considered SAEs.

Abnormal laboratory results requiring treatment or that are assessed as related to the study drug are captured as AEs. If the results of the laboratory abnormality do not require treatment and is assessed as not related to the study drug, they will not be considered AEs and will be assessed as part of safety with the laboratory assessments.

7.4. Serious Adverse Event

The ICH topic E2 on Clinical Safety Data Management, Definitions, and Standards for Expedited Reporting defines a serious adverse event (or experience; SAE) or reaction as any untoward medical occurrence that at any dose:

- Results in death
- Is life-threatening. The term "life-threatening" in the definition of "serious" refers to an event in which the patient was at risk of death at the time of the event. It does not refer to an event which hypothetically might have caused death if it were more severe.
- Requires inpatient hospitalization or prolongation of existing hospitalization of at least 24 hours.
- Results in persistent or significant disability/incapacity. The term disability means a substantial disruption of a person's ability to conduct normal life functions. This definition is not intended to include experiences of relatively minor medical significance such as uncomplicated headache, nausea, vomiting, diarrhea, influenza, and accidental trauma (e.g., sprained ankle) which may interfere or prevent everyday life functions but do not constitute a substantial disruption.
- Is a congenital anomaly/birth defect (i.e., an adverse finding in a child or fetus or a subject exposed to the study medication prior to conception or during pregnancy).
- An important medical event

NOTE: Important medical events that may not result in death, be life- threatening, or require hospitalization may be considered an SAE when, based upon appropriate medical judgment, they may jeopardize the subject and may require medical or surgical intervention to prevent one of the outcomes listed above. Examples of such medical events include allergic bronchospasm requiring intensive treatment in an emergency room or at home, blood dyscrasias or convulsions that do not result in inpatient hospitalizations, or the development of drug dependency. (FDA Guidance for Industry 1995).

Given the unique and important perspectives of both the investigator and the Sponsor, if either considers that the event is serious, the event will be considered an SAE. Serious adverse events should be reported within 24 hours of discovery. Death is an outcome of an AE/SAE rather than an SAE itself and should be reported as the antecedent proximate cause.

Disease progression (CLL/SLL/Lymphoma) resulting in death will not be captured as an SAE but will be captured on the specific CRF.

Elective hospitalizations that had been planned for starting a new treatment or for preexisting conditions that have not worsened are not considered SAEs.

7.5. Definition and Grading of Toxicities

Toxicities will be defined using NCI CTCAE v5.0 criteria. All toxicities should be graded 1-5 according to the standardized scale laid out therein.

7.6. Causality of Adverse Events

The investigator should use his or her best judgement to identify one of the following categories for causality / relatedness of the AE to the study medication.

- 1. Unrelated The Adverse Event is *clearly not related* to the investigational agent(s)
- 2. Unlikely The Adverse Event is *doubtfully related* to the investigational agent(s)
- 3. Possible The Adverse Event may be related to the investigational agent(s)
- 4. Probable The Adverse Event is *likely related* to the investigational agent(s)
- 5. **Definite** The Adverse Event is *clearly related* to the investigational agent(s).

7.7. Documentation of Adverse Events and Serious Adverse Events

7.7.1. Reporting Period

Adverse events (including SAEs) will be documented on the AE eCRF and monitored continuously throughout the study from the time of first dose of study drug until 30 days (+ 7 days) after the patient's last dose of study drug or until the event has resolved, stabilized, or an outcome has been reached, whichever comes first regardless of the timing of the End of Treatment visit. If the End of Treatment visit occurs prior to 30 days (± 7 days) after the date of last dose, then a toxicity assessment should be performed either in person or via telephone to capture AEs through the AE reporting period. In addition, SAEs occurring between the time of signing of informed consent form and the first dose of the study drug must be reported. SAEs related to the study drug and occurring after the end of the AE reporting period must be reported.

For patients who discontinue study drug due to a study-related AE, the reporting time period may be extended. These patients must be followed at least once a week for four weeks, and subsequently at four-week intervals until resolution or stabilization of the adverse event or laboratory abnormality, whichever comes first. Additionally, the frequency of AE monitoring will increase for patients who experience a DLT at the discretion of the investigator.

If the investigator considers it necessary to report an AE in a study patient occurring after the end of study, he or she should contact the Sponsor to determine how the AE should be documented and reported.

7.7.2. Assessment of Adverse Events

Investigators will assess the occurrence of AEs and SAEs at all patient evaluation time points during the study. All AEs and SAEs whether volunteered by the patient, discovered by study

personnel, or detected through physical or laboratory examination, or by any other means will be recorded in the patient's medical record and on the AE CRF.

Each assessment of AEs or SAEs will be described with the prescribed terminology including grade, with start and end (if applicable) dates, regulatory seriousness criteria (if applicable), suspected relationship to study drug, and any action(s) taken in response.

7.8. Procedures for Reporting Serious Adverse Events

All serious adverse events occurring during study participation must be reported to the Sponsor (or designee) and to the governing IRB/IEC as required by the IRB/IEC, local regulations, and the governing health authorities.

7.8.1. Completion and Transmission of SAE Report

Once an Investigator becomes aware that an SAE has occurred in a study patient, she/he will report the information to the Sponsor (or designee) within 24 hours. The eSAE form in the EDC will always be completed as thoroughly as possible with all available details of the event and submitted to the Sponsor (or designee) within the designated time frames. If the Investigator does not have all information regarding an SAE, he/she will not wait to receive additional information before notifying the Sponsor (or designee) of the event and completing the form. The form will be updated when additional information is received. Pertinent follow-up information is also reported within 24 hours of the site becoming aware of the updates.

The Investigator will provide an assessment of causality at the time of the initial report as described above. If the EDC system is not operational (e.g., system malfunction) at the time of the SAE, a paper SAE report may be completed and faxed to the Safety team. Paper SAE templates will be provided to the Investigator prior to study start.

The Sponsor will provide a list of project contacts for SAE receipt. Any event that in the opinion of the Investigator may be of immediate or potential concern for the patient's health or well-being will be reported to the Sponsor (or designee).

7.8.2. Regulatory Reporting Requirements for Serious Adverse Events

The Investigator must promptly report all SAEs to the Sponsor in accordance with the procedures describe above. Prompt notification of SAEs by the Investigator to the appropriate project contact for SAE receipt is essential so that legal obligations and ethical responsibilities towards the safety of other patients are met. The Investigator will be responsible for reporting SAEs to the IRB/IEC per local regulatory requirements.

The Sponsor (or designee) is responsible for reporting SAEs to the relevant regulatory authorities in accordance with local regulations. That is, SAEs which are "Unexpected" and classified as "Suspected Adverse Reactions" or "Adverse Reactions" will be reported.

The Sponsor (or designee) is responsible for submitting reports to the FDA of unexpected SAEs considered to be possibly related to the administration of study drug, according to 21 Code of Federal Regulations 312.32. All Investigators participating in ongoing clinical studies with the study drug will receive copies of these reports for prompt submission to their IRB/IEC. Investigators are to provide a copy of the written IRB notification for each report to the Sponsor or its designee.

An adverse event is considered "Unexpected" if it is not listed in the investigator brochure or is not listed at the specificity or severity that is observed in the present study.

[figure not shown]
7.9. Pregnancy

Pregnancy is an exclusion criterion. All patients should be instructed to immediately notify the investigator and study staff of pregnancy that occurs during the study period. Any female patient who becomes pregnant should immediately discontinue the study medication. Although pregnancy itself is not an AE, if a study patient or the partner of a study patient should become pregnant during the course of the study this should be reported on a pregnancy report form and the pregnancy should be followed to conclusion with the outcome(s) including any untoward events in mother or child reported to the study Sponsor.

[figure not shown]
7.10. Follow Up of Adverse Events and Serious Adverse Events

All AEs and SAEs occurring during the study are to receive appropriate medical treatment and be followed up in accordance with good medical practice until resolved or judged no longer clinically significant, or if a chronic condition, until fully characterized. Relevant follow-up information is to be provided to the Sponsor or its designee.

7.12. Management of Overdose and Toxicity

There are no specific treatments for overdose. In the case of accidental or intentional overdose of MS-553, standard supportive measures for overdose should be employed.

7.13. Study-wide Stopping Rule for Excessive Toxicity

To ensure patient safety, the sponsor will implement a set of study-wide stopping rules as described below.

- The sponsor shall evaluate adverse events that occur throughout the duration of therapy beyond the DLT window.
- The sponsor shall evaluate all adverse events at least quarterly throughout the study.

• The study stopping rule shall be triggered if the rate of major hemorrhage events (serious or any ≥ Grade 3 bleeding or any central nervous system bleeding) is ≥ 4.2%, the rate of major hemorrhage events listed in the product label of ibrutinib.

- The study stopping rule shall be triggered if an SAE considered to be at least possibly related to the study drug results in death.

Once a stopping rule is triggered, the study shall be paused for enrollment and a comprehensive safety review shall be conducted by the Safety Review Committee. After this review, the SRC will determine whether to recommend resuming treatment with appropriate safety measures.

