3. INVESTIGATIONAL PLAN

3.1. Overview of Study Design

This is a Phase I/II multi-center, open-label study of single agent MS-553, as well as MS-553 in combination with acalabrutinib or venetoclax and rituximab in treatment experienced CLL/SLL patients.

The study will consist of 3 cohorts. Cohort A will evaluate MS-553 monotherapy, Cohort B will evaluate MS-553 in combination with acalabrutinib, and Cohort C will evaluate MS-553 in combination with venetoclax and rituximab. A schema of the three cohorts is shown in Figure 1 in Section 3.1.4.

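### The 4.2% hemorrhage trigger is study-wide with no Series B rate, so a roughly two- to threefold bleeding excess confined to the acalabrutinib cohorts can go untriggered

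*Combined protocol and SAP*

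**What the plan says.** Section 7.13 announces that "the sponsor will implement a set of study-wide stopping rules as described below". For bleeding, the text reads "The study stopping rule shall be triggered if the rate of major hemorrhage events", with the condition that this observed rate "is ≥ 4.2%, the rate of major hemorrhage events listed in the product label of ibrutinib". The section gives no denominator, no minimum number of patients or events, no confidence bound, and no rate by cohort or series. On timing it says: "The sponsor shall evaluate all adverse events at least quarterly throughout the study". A second trigger has no denominator: the rule is also "triggered if an SAE considered to be at least possibly related to the study drug results in death". When either trigger is met, "the study shall be paused for enrollment and a comprehensive safety review shall be conducted by the Safety Review Committee"; the committee then advises whether to resume.

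Section 3.1 describes three regimens under this one rule: monotherapy (A), the acalabrutinib combination (B) and venetoclax plus rituximab (C). On the second it states: "Cohort B will evaluate MS-553 in combination with acalabrutinib". Section 3.1.2 opens Series B only after Cohort A1 has declared a dose, so monotherapy patients are already in any pooled count by then.

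**The concern.** The benchmark is a bleeding rate for a BTK inhibitor, and only Series B adds a BTK inhibitor to MS-553. Series B is therefore where an excess is most plausible, yet it is only about a quarter of the planned patients. If the study-wide rate is read as all events over all treated patients, events in Series B are divided by a denominator made up mostly of patients on other regimens. A combination that bleeds at two to three times the benchmark could then enroll to completion without the prespecified pause. The expansion cohorts B2 and B3 (about 30 patients) are the most exposed, because Section 7.1 limits DLT determination to A1, B1 and C1. For non-fatal bleeding in B2 and B3, Section 7.13 holds the only numeric trigger.

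**Working it through.** **Denominator.** The Synopsis gives about 153 patients. From the cohort descriptions:
- A2: 25 + 40 = 65. A3 is closed and counted as 0.
- B: 12 + 20 + 10 = 42, taking B1 at its upper figure.
- C: 12 + 20 = 32, taking C1 at its upper figure.
- Sum: 65 + 42 + 32 = 139. The size of A1 is not stated; 153 implies 153 − 139 = 14.

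So A = 14 + 65 = 79, Series B is 42/153 = 27%, and the other 111 patients are 79 in A and 32 in C.

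**Events needed.** The smallest r with r/n ≥ 0.042 is 1 up to n = 23, 2 up to n = 47, 3 up to n = 71, and 7 at n = 153 (6/153 = 3.9%; 7/153 = 4.6%). Six of 42 in Series B is 14.3% (exact 95% CI 5.4% to 28.5%). With no events elsewhere it does not trigger at full enrollment.

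**One look at full enrollment (exact).** P(X + Y ≥ 7), with X ~ Bin(42, pB) and Y ~ Bin(111, p0). The Series B column is P(X ≥ 2). The documents give no true rates, so pB and p0 are assumed ranges.

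| pB | pooled, p0 = 0% | 1% | 2% | Series B alone |
|---|---|---|---|---|
| 8.4% (2×) | 6% | 18% | 35% | 88% |
| 12.6% (3×) | 27% | 46% | 63% | 97.5% |
| 16.8% (4×) | 57% | 73% | 84% | 99.6% |

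**Quarterly looks (simulation).** Assumed: 39 monotherapy patients (14 + 25) treated before B and C open; the remaining 40 A, 42 B and 32 C patients accrue evenly over eight looks; events are counted at entry.

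| pB | pooled, p0 = 0% | 1% | 2% |
|---|---|---|---|
| 10% | 22% | 44% | 63% |
| 14% | 50% | 69% | 81% |

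**Series B check with at least two events.** Because 0.042 × 42 = 1.76, two events meet 4.2% at every size Series B can reach. The check therefore fires exactly when Series B has two events. At pB = 10%: 1 − 0.9^42 − 42(0.1)(0.9^41) = 1 − 0.012 − 0.056 = 93%. At 14% it is 99%.

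**Sensitivity to timing.** Accrual was varied over 36 or 60 months, event times over 3, 12 or 24 months from entry, and Series B opening after 14 or 39 monotherapy patients. Pooled trigger probabilities for p0 = 0% / 1% / 2% were:
- 2×: 6–32% / 18–52% / 36–69%
- 3×: 27–56% / 48–75% / 65–84%
- 4×: 57–78% / 74–88% / 83–93%

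**Pauses with no excess (same eight-look model).**

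| True rate everywhere | pooled alone | pooled + B, ≥ 2 events | pooled + B, ≥ 3 events |
|---|---|---|---|
| 2% | 18% | 32% | 21% |
| 1% | 3% | 9% | 4% |

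With the three-event minimum, the combined rule at 10% in B and 0–1% elsewhere triggers in about 81% of trials.

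**The case against.** A reader might infer that any large excess in Series B will usually be missed. The figures do not support that. At 14% in Series B the pooled rule triggers in half of trials or more, and at four times the benchmark it triggers in most trials under every assumption tried. With a 2% background it already triggers in 63% at 10% in Series B. A near-zero background cannot be taken for granted either, since Section 4.2 admits platelet counts down to 30 × 10^9/L, and lower with marrow involvement. The 6/153 example is also a single snapshot; quarterly looks at smaller denominators give earlier chances to trigger. All of this stands and limits the point to moderate excesses.

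A reader might also take pooling as stated. Section 7.13 says study-wide and leaves the denominator open. Pooling over all treated patients is the natural reading, but it is an inference.

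Nor would such bleeding go unreviewed. The sponsor evaluates all adverse events at least quarterly, the Synopsis (Statistical methods) describes ongoing safety review through escalation and expansion, a related death triggers the same pause, and Section 3.3.5 makes Grade 3 or higher thrombocytopenia with Grade 2 or higher hemorrhage a DLT in B1. These are real safeguards. For non-fatal bleeding in B2 and B3, however, none sets a numeric threshold or requires a pause.

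Finally, making every series a trigger would be costly. With the pooled rule kept, it pauses 50% of trials at a uniform 2% with a two-event minimum, and 71% without one. That objection is sound, and the fix is limited to Series B because of it.

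**Conclusion.** The concern holds in a limited form. Read as a pooled rate, the 4.2% rule has low sensitivity to an excess of roughly two to three times the benchmark confined to Series B. Missing it is the likelier outcome at about twofold with a background of 1% or less, and at threefold mainly when the background is near zero. Larger excesses are usually caught. The same threshold applied within Series B would detect these moderate excesses in about nine trials in ten.

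This rests on assumed true rates, an A1 size inferred from the total, upper-end B1 and C1 sizes, and assumed accrual and event timing. A smaller B1 would dilute Series B further. So would a larger C1, which Section 3.1.3 allows by giving its size per dose group where the Synopsis gives a total. The missing denominator and the absence of a series-level rate depend on none of these assumptions.

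**What to change.** In Section 7.13:
- State that the pooled denominator is all treated patients.
- Keep the pooled 4.2% rule and the pause-for-review action unchanged.
- Add the same 4.2% check within Series B, with a stated minimum number of events.
- At each quarterly review, tabulate the Series A and C rates with exact 95% CIs, for information and not as triggers.

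In the protocol this is a few sentences in one section and a short table by series at each review. The operating cost is the extra pauses shown above, and the minimum event count sets the trade-off. Two events gives 93% detection at 10% in Series B, with pauses in 32% of trials at a uniform 2%. Three events gives about 81% detection, with pauses in 21%, close to the pooled rule's own 18%. A Series B rate exactly at 4.2% would also meet the two-event check in 53% of trials at full enrollment. A pause halts enrollment for committee review and does not end the trial, so either choice is defensible if it is made in advance.

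The change does not affect the pooled rule's response to a single event at n up to 23.

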8. STATISTICAL CONSIDERATIONS AND DATA ANALYSIS

8.1. General Considerations

Summary statistics will be provided for all endpoints. Statistics will be reported according to intention-to-treat (ITT), per-protocol, and per-dose-level. The ITT summary statistics will include any patient who received at least one dose of study drug. As a phase I study, the ITT population also serves as the safety population.

Patient characteristics will be described and summarized for each dose level and in total.

8.2. Sample Size Calculations

The projected sample size was estimated on the basis of a standard 3+3 design plus a mandatory expansion cohort, plus two optional non-comparative expansion cohorts. This study is not powered to detect differences in tolerability/safety or efficacy between cohorts.

8.3. Dose Escalation Criteria

Because disease-relevant pharmacodynamics biomarkers are not yet established, and some limited toxicity and pharmacokinetic data in healthy subjects exists, dose escalation will be guided by toxicity.

8.4. Determination of Sample Size

There is no formal hypothesis to be tested in this study; therefore, no predefined sample size calculation has been made for the efficacy or exploratory endpoints.

8.5. Analysis Populations

8.5.1. Intention to Treat

The intention to treat (ITT) population shall be defined as all patients who sign the informed consent form *and* received at least one dose of study drug. This population will be used primarily for the analysis of safety data. Summary statistics for efficacy will also be performed on the ITT population.

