2.4. Primary Endpoints

The primary endpoints of this study include:

- Safety
 - The incidence rate of dose-limiting toxicities (DLT) and treatment-emergent adverse events (TEAE) requiring study drug discontinuation. Assessments for DLT and TEAE will occur during Cycle 1 for Cohort A1, and during the protocol defined DLT periods for Cohort B1 and Cohort C1 (see Sections 0 and 3.3.4). TEAE will be assessed throughout the course of the trial. The primary endpoint will be the rate of DLT and TEAE requiring study drug discontinuation in the respective DLT evaluation periods of Cohort A1, Cohort B1, and Cohort C1.
- MTD or initial RP2D as monotherapy, as well as in combination with either acalabrutinib or venetoclax and rituximab.

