3.3.2. Dose Escalation: General Principles

During the first cycle of any dose level, if ≤ 1 Dose Limiting Toxicity (DLT; as defined in Section 3.3.1) is observed, then escalation to the next higher dose level will follow the 3+3 design and proceed when 3/3 or 5/6 patients have completed one 28-day treatment cycle without a DLT. If at least 1 of 3 patients experiences a DLT at any dose level, the cohort will be expanded to 6 patients. If $\geq 2/3$ or $\geq 2/6$ patients experience a DLT within a cohort, the MTD will be considered to have been exceeded. No additional patients will be enrolled in that cohort, and dose escalation will stop. If at least 3/3 or 5/6 patients have completed one 28-day treatment cycle at the previous dose level without a DLT, then that dose may be accepted as the MTD. At Sponsor discretion, additional patients may be enrolled into a cohort where ≤ 1 patient develops a DLT to obtain additional safety, PK, PD, and/or efficacy data.

If greater than 1/6 patients experience a DLT at DL 1, then 100 mg BID may be declared the MTD, or intermediate dose levels and/or alternative dosing schedules may be evaluated upon review of safety, pharmacodynamic, and/or pharmacokinetic data.

Each dose cohort will include a minimum of 3 evaluable patients for assessment of DLT. In order to be considered evaluable for DLT, patients must meet at least one of the following criteria:

- 1. Complete dosing through the DLT period and receive at least 75% of MS-553 intended doses during that time.
- 2. Discontinue due to DLT

During the DLT evaluation period, non-evaluable patients who discontinue treatment before DLT period is complete for reasons other than study drug-related toxicities (e.g., progressive disease, non-compliance) or do not receive at least 75% of MS-553 intended doses in the DLT period, will be replaced with additional patients enrolled at the same dose level. After a DLT is resolved or reversed to \leq Grade 1, the study drug may continue at a lower dose level at the discretion of the investigator.

A decision on dose escalation to the next dose level will be based on evaluation of the clinical safety profile, and may also include evaluation of MS-553 exposure in treated patients. After the completion of each cohort, safety and PK data (if available) will be reviewed and a decision on dose escalation will be determined by the Investigators, the Safety Review Committee, and the Sponsor.

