3.3.5. Dose Limiting Toxicity Definition

Dose limiting toxicities (DLT) occurring during DLT period appropriate for the cohort will be used to determine which dose of MS-553 will be examined in expansion cohorts. Toxicities will be assessed utilizing the National Cancer Institute Common Terminology Criteria for Adverse Events (NCI CTCAE v5.0) in Appendix 4.

Dose limiting toxicities (DLT) are defined as any of the following treatment-emergent events occurring from Cycle 1 Day 1 (after administration of MS-553) through the end of the DLT period (unless the event is determined to be unrelated to the drug):

- 1. Death
- 2. Hematologic toxicities:
 - Grade 4 neutropenia for \geq 7 days
 - Grade 3 febrile neutropenia: absolute neutrophil count (ANC) <1000/mm³ and single temperature >38.3°C (101°F) or a sustained temperature ≥38°C (100.4°F) for > 1 hour
 - Grade 4 thrombocytopenia \geq 14 days (patients with baseline platelet count of \geq 50 x 10⁹/L)
 - Grade 4 thrombocytopenia ≥ 28 days (patients with baseline platelet count < 50 x $10^9/L)$
 - \geq Grade 3 thrombocytopenia associated with \geq Grade 2 hemorrhage
 - New ≥ Grade 3 anemia requiring transfusion in a patient previously transfusionindependent.
- 3. Nonhematologic toxicities:
 - Any other ≥ Grade 3 toxicity not reversed to any one of the following three conditions in 7 days with appropriate intervention: a) baseline; b) ≤ Grade 1; or c) a status considered to be controlled by the Safety Review Committee (For example, isolated ≥ Grade 3 laboratory toxicity [e.g., electrolyte abnormalities] not associated with clinical signs or symptoms and is reversed to Grade 2 with appropriate intervention in 7 days is not considered a DLT.)
 - Any treatment-related adverse event (TEAE) requiring >25% of doses of scheduled study drug to be withheld during the DLT period.

All patients will continue to be monitored for approximately 30 days (+7 days) after treatment discontinuation for development of any late treatment emergent adverse events. Any such late adverse events will be considered in the determination of the MTD/initial RP2D and dose schedule to be taken forward into the expansion phase of the study.

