6.2. Assessments of Safety, Efficacy, and Exploratory Endpoints

6.2.1. Safety

For Cohort A1, assessments for DLT and TEAE will occur during Cycle 1. For Cohort B1 and C1, assessments for DLT and TEAE will occur during defined DLT evaluation periods (see Sections 0 and 3.3.4). TEAE will be assessed during the course of the trial. The primary endpoint will be the rate of DLT and TEAE requiring study drug discontinuation in the DLT evaluable period.

Toxicities will be defined using NCI CTCAE v5.0 criteria in Appendix 4.

Safety assessments will consist of monitoring and recording all adverse events, including serious adverse events, the monitoring of hematology, blood chemistry, and the regular monitoring of vital signs, ECGs, and physical condition as shown in Appendix 1A (A Cohorts), 1B (B Cohorts), or 1C (C Cohorts). For details on AE collection and reporting, refer to Section 7, Adverse Events and Toxicity Management. If a patient has vision-related adverse event that is \geq Grade 2 and deemed at least possibly related to the drug, the patient will be referred to an ophthalmologist for a typical 8-point exam including measurement of visual acuity, slit-lamp bio-microscopy, and dilated full-fundus examination of the macula, optic nerve and peripheral retina.

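### Safety is analysed on all dosed patients and Section 8.5 has no DLT-evaluable set, so the DLT part of the primary endpoint can be understated when patients are replaced

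*Combined protocol and SAP*

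**What the plan says.** The primary safety endpoint covers Cohorts A1, B1 and C1. Section 2.4 has: "The primary endpoint will be the rate of DLT and TEAE requiring study drug discontinuation in the respective DLT evaluation periods". Section 6.2.1 has: "The primary endpoint will be the rate of DLT and TEAE requiring study drug discontinuation in the DLT evaluable period". Both give a time window; neither gives a denominator.

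Section 8.1 promises summary statistics for every endpoint, by ITT, per protocol and per dose level, and adds: "As a phase I study, the ITT population also serves as the safety population". Section 8.5.1 defines ITT as "all patients who sign the informed consent form *and* received at least one dose of study drug", and continues: "This population will be used primarily for the analysis of safety data". The statistical methods part of the synopsis likewise bases the safety summaries on anyone dosed. The other sets in Section 8.5 are per-protocol, pharmacokinetic and pharmacodynamic. Sections 8.8 and 8.9 cover secondary efficacy and exploratory analyses; no section is given to the primary endpoint.

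The dose-escalation text works with a different set. Section 3.3.2 states: "Each dose cohort will include a minimum of 3 evaluable patients for assessment of DLT". A patient is evaluable either by finishing the DLT window with three quarters or more of the planned MS-553 doses, or by stopping because of a DLT. Non-evaluable patients who leave early for reasons other than drug toxicity, or who fall short on doses, "will be replaced with additional patients enrolled at the same dose level". One of the DLT criteria in Section 3.3.5 is: "Any treatment-related adverse event (TEAE) requiring >25% of doses of scheduled study drug to be withheld during the DLT period".

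**The concern.** A patient who is dosed and then replaced stays in the ITT set. If that patient left after two weeks for progression, most of the DLT window was never observed, yet the patient counts as DLT-free in an all-dosed rate. The reported DLT rate would then differ from the rate on which the dose was chosen, and the difference would grow with the number replaced. Cohort C1 is the most exposed: its window is four cycles (16 weeks) against one 28-day cycle in A1 and B1.

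The per-protocol set is no substitute. It requires a full course ending at progression or at the maximum number of cycles, so it leaves out patients who stop for toxicity. No listed set matches the patients used for escalation.

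The endpoint also joins two events that need different denominators. TEAE discontinuation is naturally counted in all dosed patients. On an evaluable-only set, a patient who stops mid-window for an unrelated TEAE would disappear from both numerator and denominator.

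**Working it through.** **Inputs.** From Section 3.3.2: cohorts of 3 or 6, escalation at 3/3 or 5/6 without a DLT, MTD exceeded at 2 or more DLTs. From the synopsis and Table 5: a 16-week window in C1. The documents give no target DLT rate, no expected share of non-evaluable patients and no formal hypothesis, so there is no plan figure to reproduce. The numbers replaced below are assumptions.

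**Step 1, DLT component.** With x DLTs in 6 evaluable patients and r replaced patients without a DLT, the evaluable rate is x/6 and the all-dosed rate is x/(6 + r).

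| r (assumed) | x = 1 | x = 2 |
|---|---|---|
| 0 | 1/6 = 16.7% | 2/6 = 33.3% |
| 1 | 1/7 = 14.3% | 2/7 = 28.6% |
| 2 | 1/8 = 12.5% | 2/8 = 25.0% |
| 3 | 1/9 = 11.1% | 2/9 = 22.2% |

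The exact 95% interval moves too: 0.4 to 64.1% for 1/6, and 0.3 to 52.7% for 1/8. With no DLTs the estimate stays at 0%, but the upper limit falls from 70.8% (0/3) to 60.2% (0/4) on the strength of a patient not fully observed.

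**Step 2, general form.** If a share d of dosed patients is non-evaluable and has no DLT, a rate p becomes p(1 − d). For d = 5%, 10%, 20% and 30% (assumed range), 16.7% becomes 15.8%, 15.0%, 13.3% and 11.7%.

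**Step 3, effect of the longer window.** At an assumed 5% non-toxicity loss per 28 days, d is 5% in B1 and 1 − 0.95^4 = 18.5% in C1. At 10% it is 10% and 1 − 0.90^4 = 34.4%. A DLT rate of 16.7% would then read 15.8% in B1 and 16.7% × 0.815 = 13.6% in C1 at 5% loss, or 15.0% and 16.7% × 0.656 = 10.9% at 10% loss.

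**Step 4, composite.** Let y of r non-evaluable patients have a TEAE discontinuation that is not a DLT. The all-dosed composite is (x + y)/(6 + r), and it exceeds x/6 exactly when y/r exceeds x/6. With x = 1, r = 1, y = 1 it is 2/7 = 28.6% against 16.7%, so it rises. With y = 0 it falls, as in Step 1.

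**Step 5, can the Section 3.3.2 criteria be copied as they stand?** Take a patient whose DLT is that more than 25% of doses were withheld for a related event. That patient received less than 75% of doses and so fails the first criterion. Section 3.3.2 allows treatment to go on at a lower dose once a DLT has resolved; a patient who does so has not stopped because of it and fails the second criterion as well. Read literally, a patient with a DLT is non-evaluable and is replaced. An analysis set built on that text unchanged would lose a DLT.

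**The case against.** The case against has several sound parts.

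- **The concept is not missing.** Section 3.3.2 defines evaluability and ties DLT assessment to it, and the word "primarily" in Section 8.5.1 leaves some room. That makes the fault a missing link between Sections 3.3.2 and 8.5. It does not remove the fault: Section 8.1 covers every endpoint with the listed sets, and the synopsis has no such qualifier.
- **Dilution is not certain.** It needs the all-dosed set to be used, at least one DLT, and at least one replaced patient without a DLT. It concerns the DLT component; Step 4 shows that the composite has no fixed direction.
- **Dose decisions.** A reader might infer that 2/9 = 22.2%, being under one third, could hide an exceeded MTD. The documents do not support this. The rule in Section 3.3.2 is a count of DLTs applied during escalation, and nothing compares an ITT percentage with one third.
- **An evaluable-only set loses fewer events than it may seem.** A related event that stops the drug early enough to cost more than 25% of doses is, on a natural reading, itself a DLT. What drops out is unrelated TEAE discontinuations and related non-DLT stops late in the window.
- **The TEAE label.** Section 3.3.5 attaches the abbreviation to treatment-related events, while Section 2.4 and the abbreviation list use it for treatment-emergent ones. This is editorial: the opening of the DLT definition already excludes events judged unrelated.
- **Partial cover.** Section 8.1 already gives results by dose level and Section 8.7 gives 95% CIs for selected categorical endpoints, though neither names the DLT rate.

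**Conclusion.** The point stands in a limited form. Followed literally, the plan reports the DLT component of its primary endpoint on all dosed patients, while DLT assessment rests on evaluable ones. With two replaced patients the fall is from 16.7% to 12.5%. Over one to three replacements the all-dosed rate runs from 14.3% down to 11.1%. These sizes rest on assumed replacement counts and on replaced patients having no DLT.

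It would go too far to say that the primary endpoint is biased downward, since the composite can also rise, or that escalation is compromised, since 3+3 decisions made on evaluable patients do not depend on the Section 8 denominator. The statistics are descriptive and the intervals are wide. What is at stake is whether the reported DLT rate means the same as the one used to select the dose.

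**What to change.** 1. Add a DLT-evaluable population to Section 8.5 by reference to Section 3.3.2, stating that any patient with a DLT in the window belongs to it.
2. Reconcile the evaluability and replacement wording in Section 3.3.2 (and the matching synopsis text) with the withheld-dose DLT in Section 3.3.5.
3. In Sections 2.4 and 6.2.1 report two rates separately: (a) the DLT rate on the DLT-evaluable population; (b) the rate of treatment-emergent AEs leading to MS-553 discontinuation in the DLT period on all dosed patients. Give each by dose level with an exact 95% CI, and state the number of patients replaced.
4. As an editorial correction, drop the TEAE abbreviation from the treatment-related criterion in Section 3.3.5.

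This takes wording changes to the protocol and its statistical section, with no additional analysis data. The downside is that the reported DLT rate may be slightly less favourable.
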